	
 
• Mean serum ALT, aspartate aminotransaminase (AST), bilirubin, albumin and gamma-glutamyl transpeptidase (GGT) at Weeks 4, 8, 12, 16, 20 and 24
 
• Proportion of subjects whose ALT at Week 24 is within the normal reference range defined as <math>\leq 19</math> IU/L for women and <math>\leq 30</math> IU/L for men.
 

Exploratory outcome measures	
 
• Mean serum concentrations of: lipopolysaccharide (LPS), C-reactive protein (CRP), cytokeratin (CK)-18 fragments, glucagon-like peptide (GLP)-1 and adiponectin and subsets of inflammatory cytokines: interleukin (IL)-6, IL-1<math>\alpha</math>, IL1<math>\beta</math>, IL-2, IL-3, IL-4 IL-10, IL-13, IL-12, IL-17<math>\alpha</math>, IL-23 interferon gamma (IFN<math>\gamma</math>), Transforming Growth Factor Beta (TGF-<math>\beta</math>) and tumor necrosis factor alpha (TNF<math>\alpha</math>)
 
• Serum metabolomics
 
• Relative levels of regulatory T cells in peripheral blood mononuclear cells (PBMC) samples, including CD4, CD8, CD25, FoxP3, NKT, CD62 and CD69 T cells;
 
• Characterization of the gut microbiome
 
• Explore a dose effect
 

Study design:	This is a randomized, double blind, placebo controlled, 3-arm parallel group, multi-dose, multi-center study.
Study duration / participant:	Up to 45 days for Screening and 24 weeks of treatment.  Subjects terminating study drug will be followed-up post-treatment for 28 days.
Number of participants:	At least 120, randomized 1:1:1  Treatment allocation will be stratified by the following: 
 
• Baseline MRI Liver Fat, according to the following scale: <math>\leq 10\%</math>, <math>10\% < X \leq 20\%</math>, <math>20\% < X < 30\%</math> and <math>\geq 30\%</math>
 
• Diabetic status defined as being normal (HBA1C <math>\leq 6.0</math>) or diabetic (having a diagnosis of Type II diabetes and/or HBA1C <math>> 6.0</math> and <math>\leq 9.0</math> whether or not receiving allowable medication).
 

Study drug:	IMM-124E 600mg tablet
Control group:	Placebo to match
Dose Regimens	Arm A: IMM-124E 600mg three times daily; Arm B: IMM-124E 1200mg three times daily; Arm C: Matching placebo three times daily.  All treatment dose regimens are administered per orally

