## 8. STUDY DRUGS

### 8.1 Randomization

Subjects will be randomized to one of three treatment groups using a permuted block randomization algorithm supplied by a statistician blinded to patient data.

NASH without insulin resistance or diabetes may be clinically different to NASH with pre-diabetes or diabetes. Equal numbers of patients in each treatment arm is targeted. Randomization will be proportional (1:1:1) and stratified by Baseline HBA1C  $\leq 6.0$  or  $>6.0 - 9.0$ . (See [Section 7.2.2](#) and the Study Reference Manual)

Additionally, to ensure baseline Hepatic Fat Fraction (HFF) would not be a confounding factor, subjects will be stratified for baseline HFF according to the following groups  $\leq 10\%$ ,  $10\% < X \leq 20\%$ ,  $20\% < X < 30\%$  and  $\geq 30\%$ .

If a subject discontinues from the study, the randomization code will not be reused, and the subject will not be allowed to re-enter the study.

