2.2 Study design

This was to be a randomized, double blind, placebo controlled, 3-arm parallel group, multi-dose, multi-centre study. The three treatment arms include 600mg IMM-124E three times daily, 1200mg IMM-124E three times daily and matching placebo. A total of 120 subjects, randomised to the three treatment groups in 1:1:1 ratio, having been previously diagnosed with NASH will be studied during a 24 week treatment period.

An interim analysis will be planned for this study, the purpose of which will be to determine whether any safety concerns exist as well as identify any preliminary signals for efficacy through examination of the primary, secondary and exploratory endpoints. The interim analysis will occur when 80 subjects have completed the 24 weeks treatment period and have both Baseline and 24 weeks' evaluable MRI hepatic fat fraction values. Each IMM-124E dose group will be compared to the placebo treatment group using pairwise contrasts. This analysis will occur for each of the hepatic fat fraction strata because of a differential response pattern across strata that have been noticed in previous studies on NASH (Le et al., 2012; Loomba et al., 2015).

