3. ANALYSIS POPULATIONS AND GENERAL STATISTICAL METHODOLOGY

This analysis plan is based on version 1.3 of the protocol, dated 8 May 2016, and includes other changes discussed at a later date.

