7.2 Primary efficacy analyses

The hepatic fat fraction will be summarised and tabulated for the Baseline and Week 24 visits along with change from Baseline by randomised treatment group. Change in hepatic fat fraction from Baseline will be analysed using analysis of variance on the ITT, PP and FAS populations, where the model will include the treatment group and another subgrouping variable. As determined by baseline values, hepatic fat fraction categories ($\leq 10\%$, $>10\% - <21\%$, $\geq 21\% - <30\%$ and $\geq 30\%$), HbA1c group ($< 6\%$ and $\geq 6\%$), and ALT (greater or less than 1.5 x the upper normal limit) will be used to subgroup the analysis populations. Further, data from liver biopsies up to 6 months prior to screening will also be used to subgroup analysis populations based on fibrosis (0-1 vs. 2-3), NAS inflammation (0-1 vs. 2-3), and NAS ballooning (0-1 vs. 2). These will be used in addition to the main effects factors and the two-way interaction of those main effects.

In the primary analysis, any missing data will remain missing. Treatment effects between placebo and each of the active treatment groups within each of the hepatic fat and HbA1c categories will be generated and tested for significant differences between treatment and placebo using pre-specified contrasts.

To examine the effect of treatment within the various levels of these subgroup variables, a mixed models ANOVA will be employed if there are an appropriate number of observations in each cell (created by the crossing of study treatment and subgroup categories) and the data does not differ significantly from a normal distribution. In the event that this is not the case, the data will be ranked in an attempt to normalise it, and pairwise contrasts between treatment groups will be performed using Wilcoxon rank sum tests within each combination of visit and subgroup variable level will be performed. However, if the ranked data is also not normally distributed, a permutation test will be employed whereby the unranked data will be randomly sampled (Lehmann, 2006). No adjustment for multiple testing will be made. See Appendix 1 for more information on both the Wilcoxon rank-sum test and the permutation test.

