9. INTERIM ANALYSES

An interim analysis is planned when 80 subjects have completed the full 24 week study period. The analysis population will include data from those 80 subjects up to and including week 24, in addition to all early terminations (up to and including week 24) and all remaining currently randomised subjects with post-baseline data prior to the 28th of February 2017. Populations in the interim analysis will use the same definitions as the full analysis at the end of the study.

The purpose of this interim analysis will be to establish the safety of the study treatment, identify signals of efficacy of the two dose groups (600mg and 1200mg) against Placebo and to set sample size parameters for potential future studies. As a result, the critical probability for the interim analysis will be 0.00305, which requires the final alpha level to be 0.04695. All populations will be analysed for the interim analysis as described above.

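### SAP 7.2 moves the middle liver-fat boundary from 20% to 21% and puts HbA1c of exactly 6.0 in the other group, so the analysis categories are not the randomisation strata; no reason is given

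*SAP*

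**What the plan says.** **Randomisation.** Protocol 8.1 states that "subjects will be stratified for baseline HFF according to the following groups" ≤10%, above 10 to ≤20%, above 20 to below 30%, and ≥30%. The synopsis lists the same four groups. For the second factor, 8.1 says "Randomization will be proportional (1:1:1) and stratified by Baseline HBA1C" ≤6.0 or above 6.0 to 9.0. The synopsis instead uses diabetic status: normal is HbA1c ≤6.0, "or diabetic (having a diagnosis of Type II diabetes and/or HBA1C" above 6.0 and up to 9.0.

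**Analysis.** SAP 7.2 keeps the outer HFF cuts of 10% and 30% but sets the middle ones, and the HbA1c groups, as ">10\% - <21\%$, $\geq 21\% - <30\%$ and $\geq 30\%$), HbA1c group ($< 6\%$ and $\geq 6" and above. Effects of each dose against placebo "within each of the hepatic fat and HbA1c categories will be generated and tested for significant differences between treatment and placebo using pre-specified contrasts". No multiplicity adjustment is made. SAP Appendix 1 uses the baseline fat-fraction categories as clusters for its rank test.

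**Interim.** SAP 2.2 says "This analysis will occur for each of the hepatic fat fraction strata because of a differential response pattern across strata" seen in earlier NASH studies. SAP 9 sets the thresholds: "the critical probability for the interim analysis will be 0.00305, which requires the final alpha level to be 0.04695".

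**Explanation of changes.** SAP 3 says that the plan rests on protocol version 1.3 and "includes other changes discussed at a later date". SAP 10 leaves departures from the protocol to the final study report.

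**The concern.** A patient can be randomised in one group and analysed in another. SAP 2.2 calls the HFF groups strata, and the SAP table list describes them as a stratification factor, so a reader would take a by-stratum result to refer to the randomised stratum. SAP 2.2 explains why results are examined by HFF group. It does not explain why the boundary moved.

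What is at stake is limited to the within-category contrasts. There the cut decides which patients enter a contrast and sometimes whether it crosses the threshold. An unexplained one-point shift also invites the question of how the cut was chosen.

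The diabetes wording is a second problem. Read literally, a patient with a Type II diagnosis and HbA1c ≤6.0 fits both synopsis groups, while 8.1 places that patient in the lower stratum. The documents do not show which rule the randomisation system applied.

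**Working it through.** **1. The plan's own figure.** Protocol 12.1 assumes an SD of 6% at each timepoint and a pre/post correlation of 0.25. SD of change = √(6² + 6² − 2 × 0.25 × 6 × 6) = 7.35 (stated: 7.3). With 40 per arm, a difference of 5 and SD 7.3, power is 0.865 by the normal approximation and 0.857 by the noncentral t with 78 df. The stated 85% is reproduced. It ignores stratification, so this point does not alter it.

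**2. Who changes group.**

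| Variable | Randomisation (8.1) | SAP 7.2 | Values that change group |
|---|---|---|---|
| HFF, middle boundary | ≤20 / >20 | <21 / ≥21 | strictly between 20 and 21: 20.1 to 20.9 if recorded to 0.1; none in whole percents |
| HbA1c | ≤6.0 / >6.0 | <6 / ≥6 | exactly 6.0 (recorded to 0.1) |

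**3. How many.** The documents give no baseline means and no recording precision, so these are assumptions.

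- HFF to 0.1, normal, SD 6: share = Φ((20.95 − m)/6) − Φ((20.05 − m)/6).

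| Assumed mean m (%) | Share | Of 120 |
|---|---|---|
| 14 | 0.033 | 4.0 |
| 16 | 0.045 | 5.4 |
| 18 | 0.055 | 6.6 |
| 20 | 0.060 | 7.1 |
| 22 | 0.058 | 7.0 |

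 Counts use unrounded shares. At the 80-patient interim the range is 2.7 to 4.8.
- HbA1c to 0.1, normal, mean 5.8–6.6, SD 0.6–1.0: share = Φ((6.05 − m)/s) − Φ((5.95 − m)/s) = 0.033 to 0.066, or 4.0 to 8.0 of 120.

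**4. Effect on the HFF contrasts.** Null simulation, 5,000 trials per setting. Assumptions: HFF mean 14, 18 or 22, SD 6, recorded to 0.1; HbA1c mean 6.2, SD 0.8; blocks of 6 within HFF × HbA1c strata by the 8.1 cuts; pre/post correlation 0.25. Two-sample t-tests within a category stand in for the SAP model. Four contrasts are affected: the two middle categories, each with two doses.

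| Result (HFF mean 14 / 18 / 22) | Final: N=120, α=0.04695 | Interim: N=80, α=0.00305 |
|---|---|---|
| At least one of four changes status | 11.5 / 11.7 / 12.0% | 1.2 / 0.8 / 1.0% |
| At least one lost on moving to 21 | 5.4 / 6.5 / 6.1% | 0.7 / 0.5 / 0.5% |
| At least one gained | 6.5 / 5.5 / 6.2% | 0.5 / 0.3 / 0.5% |

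The Monte Carlo SE of the first row is 0.5 points at the final analysis and 0.1–0.2 at the interim. Rejection per contrast at the final analysis, 20 cut against 21 cut, is 4.4/4.7%, 4.9/4.6% and 4.6/4.7%.

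**5. Effect on the overall comparison.** Separate null simulation of change on treatment plus HFF category, N=120, α=0.04695, 20 cut against 21 cut. The mean effect is within 0.03 of zero under both. The SD of the effect is 1.394/1.399, 1.405/1.415 and 1.371/1.372. Rejection is 4.9/5.0%, 5.1/5.0% and 4.8/4.9%. The two cuts are practically indistinguishable.

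**The case against.** The strongest reply is that SAP 7.2 presents these variables as subgroups, that protocol 12.4 leaves subgroup specification to the SAP, and that subgroup cuts need not match randomisation strata. Since both groupings use baseline values only, what remains would be a missing explanation. That is right for the overall test, and it is why the point is minor.

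Three limits on the figures stand:

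- In whole percents the two sets of HFF categories are identical, so the HFF half may have no effect. The HbA1c mismatch at 6.0 remains.
- HFF stratification came in with Amendment 3. Anyone randomised earlier had no HFF stratum to be moved from, so 4–7 is an upper bound for patients analysed outside their randomised HFF stratum. The documents do not give the number randomised earlier.
- The 11.5–12.0% is for any of four contrasts; per contrast it is about 3.3–3.5%. Gains and losses balance, so it reflects the instability of small unadjusted tests and does not show that 21 is the worse cut. The simulation does not model the SAP's rank and permutation fallback for thin cells. No simulation was made for the HbA1c contrasts.

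Protocol 12.5.1 makes analysis by diabetes status descriptive only. That does not remove the point, because SAP 7.2 does test within HbA1c categories; it is a further discrepancy between the documents. On the diabetes definition, the Study Reference Manual cited in 8.1 may settle the rule, and the synopsis can be read so that a diagnosis overrides the HbA1c value. The two protocol passages still differ.

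**Conclusion.** The concern holds at minor severity. The difference in cut-points, the absence of a stated reason and the two definitions of the diabetes stratum are certain from the text. Their numerical effect depends on the assumed baseline distributions and recording precision. In a trial that protocol 12 calls exploratory, the consequence is that a few boundary patients can shift an unadjusted per-category contrast in either direction, rarely at the interim, and that a result labelled by stratum may not describe the randomised stratum. The overall treatment comparison is not at risk.

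**What to change.** - In SAP 7.2, and so in the categories that Appendix 1 uses, adopt the randomisation cuts: HFF ≤10, >10 to ≤20, >20 to <30, ≥30; and HbA1c ≤6.0 against >6.0, or the diabetes stratum that the randomisation system actually used.
- Apply the same HFF cuts to the baseline values of anyone randomised before Amendment 3.
- Reconcile the synopsis and protocol 8.1 to the one diabetes-stratum definition that was used.
- Keep a 21% or below-6 cut only as a labelled additional subgroup, fixed before unblinding.

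The cost is very small: corrected cut-points in one SAP section and one aligned line of protocol text. No new data, patients or analyses are needed.

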
Sample size determination:
	
Fat Liver Content Change from Baseline:                  The current sample size of 40 subjects per group should yield approximately 85% power to detect a treatment effect of at least -5% with respect to the difference in the mean change from Baseline between one of the IMM-124E treatment groups and placebo assuming a standard deviation (SD) of 7.3% (<math>\alpha=0.05</math>; two-tailed; unpaired t-test). The SD of 7.3% for the change from Baseline endpoint was derived assuming 1) SDs of 6% for each timepoint, 2) equal variances in each treatment group and 3) a low to moderate correlation of 0.25 between pre- and post-Baseline measurements.
 
Sample size and power estimates have not been adjusted for multiple comparisons or multiple endpoints, dropouts or stratification.
 
The analysis of each primary endpoint will be based on a linear model that incorporates the baseline measure as a covariate, the stratification factor and randomized treatment group. Pairwise comparisons of each active treatment group to control will be conducted via linear contrasts.

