#### Fat Liver Content Change from Baseline:

The current sample size of 40 subjects per group should yield approximately 85% power to detect a treatment effect of at least -5% with respect to the difference in the mean change from Baseline between one of the IMM-124E treatment groups and placebo assuming a standard deviation (SD) of 7.3% ( $\alpha=0.05$ ; two-tailed; unpaired t-test). The SD of 7.3% for the change from Baseline endpoint was derived assuming 1) SDs of 6% for each timepoint, 2) equal variances in each treatment group and 3) a low to moderate correlation of 0.25 between pre- and post-Baseline measurements.

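### SAP 7.2 gives only an interaction model for the primary endpoint and leaves the overall dose-placebo contrast undefined; under default equal weighting, sparse liver-fat strata would drive it

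*SAP*

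**What the plan says.** SAP 7.2 analyses change in hepatic fat fraction (HFF) by analysis of variance, "where the model will include the treatment group and another subgrouping variable". It lists six such variables: HFF category (four levels, cut at 10, 21 and 30%), HbA1c, ALT, fibrosis, inflammation and ballooning. It then adds: "These will be used in addition to the main effects factors and the two-way interaction of those main effects". The contrasts it specifies are each dose against placebo within the HFF and HbA1c categories. It gives no formula or weights for a difference across categories, and continuous baseline HFF is not in the model.

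The protocol synopsis specifies a different model, a "linear model that incorporates the baseline measure as a covariate, the stratification factor and randomized treatment group", with pairwise linear contrasts and no interaction. SAP Section 10 leaves changes from the protocol to be documented in the final study report.

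The sizing (Protocol 12.1) reads: "The current sample size of 40 subjects per group should yield approximately 85% power to detect a treatment effect of at least -5" percentage points, "assuming a standard deviation (SD) of 7.3". That SD is built from "SDs of 6% for each timepoint" and "a low to moderate correlation of 0.25 between pre- and post-Baseline measurements". The synopsis states that power was not adjusted for dropout or stratification.

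**The concern.** Once a treatment-by-stratum interaction is fitted, there is no single treatment coefficient. An overall difference is a weighted average of stratum differences, and the weights have to come from somewhere. If the SAP is silent, a programmer is likely to accept the software default for adjusted means, which commonly weights strata equally. A stratum holding 5% of subjects would then count as much as one holding half. The contrast could not be estimated if a stratum lacked either dose or placebo subjects, and it would describe a population spread evenly over the four fat bands.

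At stake is the trial's main result, the overall dose-placebo difference in liver fat. Adding the baseline covariate would not cure this if the interaction stayed and the weights remained unstated.

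**Working it through.** **The plan's own figure.** SD of change = √(6² + 6² − 2·0.25·6·6) = √54 = 7.35, stated as 7.3. With 40 per arm, SE = 7.3·√(2/40) = 1.63 and 5/1.63 = 3.06. Power ("two-tailed; unpaired t-test", alpha 0.05) is 85.7%, or 85.0% at the SAP's final alpha of 0.04695. The stated 85% is reproduced.

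**Stratum sizes.** The documents give no mean baseline HFF, so it is varied. Assume a normal baseline with SD 6, the SAP cut-points and 40 per arm. At every mean tried from 10 to 26, the smallest stratum expects at most 1.9 subjects per arm.

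**Equal-weight contrast.** SE = σ·√[(1/16)·Σ(1/n_dose + 1/n_placebo)] over the four strata. At mean 20, Σ1/n = 1/1.91 + 1/20.74 + 1/15.44 + 1/1.91 = 1.16 per arm. So SE = σ·√(2·1.16/16) = 0.381σ, against 0.224σ unstratified, a ratio of 1.70.

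Two values of σ are used. One is 7.3. The other is the within-stratum SD implied by the protocol's inputs, √[36(1 − 0.25²) + (0.25 − 1)²·v], where v is the average within-stratum baseline variance. At mean 20, v is about 7.0, which gives 6.14.

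| Mean | Expected per arm, lowest to highest stratum | SE ratio | Power, σ = 7.3 | Power, implied σ |
|---|---|---|---|---|
| 15 | 8.1 / 25.6 / 6.1 / 0.25 | 3.30 | 15% | 19% |
| 18 | 3.7 / 24.0 / 11.4 / 0.9 | 1.94 | 35% | 46% |
| 20 | 1.9 / 20.7 / 15.4 / 1.9 | 1.70 | 43% | 56% |
| 22 | 0.9 / 16.4 / 19.0 / 3.7 | 1.93 | 35% | 47% |

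**Simulation.** Fractional expected counts are only a guide, so trials were simulated: 120 subjects, 1:1:1, a true effect of −5 in every stratum, no dropout, permuted blocks of 6 (block size assumed). Inestimable means that a stratum is present but has no subjects in the dose or the placebo arm.

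- Blocks within liver-fat by HbA1c strata (HbA1c split evenly, assumed), means 18 / 20 / 22: inestimable in 53 / 32 / 54%. Power when estimable is 56 / 53 / 57% with the implied σ and 43 / 42 / 44% with σ = 7.3.
- Blocks within liver-fat strata only, means 18-22: inestimable in about 20-47%, with power when estimable of 54-59% (implied σ).
- Means 15 and 25, first scheme: inestimable in about 49%. Power when estimable is 79% and 87% (implied σ), or 66% and 72% (σ = 7.3). It is higher here because one stratum is absent altogether in about 46-47% of trials, and the average then runs over three strata.
- Wider baseline SD: power about 61-79% at SD 8 and 72-85% at SD 10.

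**Comparators.** With the implied σ and mean 20, treatment plus stratum without interaction has about 95% power. Keeping the interaction but weighting strata by observed size also gives about 95%. With continuous baseline as covariate, residual SD = 6·√(1 − 0.25²) = 5.81 and power is about 97%. The like-for-like comparator for the σ = 7.3 figures is about 86% (unstratified, pooled error).

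**Weighting effect alone.** With assumed stratum shares of 10/45/35/10%, the variance factor is (1/16)(1/0.10 + 1/0.45 + 1/0.35 + 1/0.10) = 25.08/16 = 1.57. That takes 85% power to about 67-68%.

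**The case against.** The strongest case on the other side has four parts.

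1. Equal weighting appears nowhere in the documents. This is correct, and it limits the claim. The loss comes from the weights, not from the interaction term, and observed-size weights remove nearly all of it. But the SAP does not ask for those weights.

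2. SAP Section 12 lists an analysis of change in HFF separately from the subgroup tables and has separate shells for the primary analysis with and without subgrouping. This suggests that an overall analysis without subgroups is intended. It does not supply a model: 7.2 describes none without a subgrouping variable, and the primary shell includes adjusted changes and between-arm differences whose source is not stated.

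3. Sparse cells are provided for. SAP 7.2 moves to ranks, Wilcoxon or permutation tests when cells are too thin, and Appendix 1 defines a rank-sum test stratified by fat category. Simulated with a normal approximation at alpha 0.04695 and baseline SD 6, that test had 87-91% power at means from 15 to 25. So a valid test remains available. It does not estimate the mean difference named as the primary outcome. The trigger, an appropriate number of observations, is undefined, and the route is introduced for effects within subgroup levels.

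4. Liver fat is only one of six candidate factors, and the other five are binary. With an assumed 30/70 split, equal weighting costs a variance factor of only (1/4)(1/0.3 + 1/0.7) = 1.19. This stands: the large losses belong to the four-level liver-fat factor. It also means that the overall contrast changes with the factor chosen, and the SAP does not choose one.

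**Conclusion.** The point holds as a gap in specification with a potentially large consequence. The only model in SAP 7.2 for the primary endpoint carries an interaction that the protocol model lacks, drops the protocol's baseline covariate, and comes with no rule for forming the overall dose-placebo difference.

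The size is conditional on three things: liver-fat category as the factor, equal weights, and baseline SD 6 with a mean of 18 to 22. The contrast is then inestimable in roughly 20-55% of trials and has about 42-59% power when estimable, against about 95% without the interaction (about 86% where the residual SD is 7.3). A normal baseline, a common effect across strata, blocks of 6 and no dropout are also assumed.

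A reader might infer that the SAP prescribes an equal-weight average and so halves the trial's power, or that the primary contrast is almost certain to be inestimable when the mean is near 15 or 25. The documents do not support either reading. No weights are stated, the planned tables point to a separate overall analysis, and SD 6 is a sizing assumption. A halving does not hold across plausible inputs. At means of 15 or 25 a stratum is often missing from the whole trial, which changes the average but does not prevent an estimate.

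**What to change.** In SAP 7.2, state that the overall dose-placebo contrasts, those reported in the primary analysis table, come from the protocol model: treatment and stratification-factor main effects plus continuous baseline HFF, with no treatment-by-subgroup interaction. State that the interaction model is used only for the within-subgroup tables. If one model must serve both purposes, specify that the overall contrast weights strata by their observed sizes.

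The cost is a few sentences of SAP text and one additional model call. No new data are needed. The change should be made before unblinding.

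### Under the plan's own SD of 6 points and a roughly normal baseline, at least one outer liver-fat category would hold about 2 or fewer patients per arm, too few for the planned dose-versus-placebo test inside it

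*SAP*

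**What the plan says.** SAP 7.2 divides baseline HFF into four categories: up to 10%, above 10 to below 21%, 21 to below 30%, and 30% or more. Effects of each dose against placebo within the "hepatic fat and HbA1c categories will be generated and tested for significant differences between treatment and placebo using pre-specified contrasts", with no multiplicity adjustment. For the interim at 80 completers, SAP 2.2 says: "This analysis will occur for each of the hepatic fat fraction strata because of a differential response pattern across strata".

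SAP 7.2 uses a mixed-model ANOVA if the treatment-by-category cells are large enough (no number is given) and the data are close to normal. Otherwise it moves to Wilcoxon rank-sum tests within each subgroup level, and then to a permutation test. Appendix 1 describes a different rank test, which ranks within each HFF category and sums over categories to one statistic per dose.

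The sample size in Protocol 12.1 covers whole arms only: "The current sample size of 40 subjects per group should yield approximately 85% power to detect a treatment effect of at least -5" points, "assuming a standard deviation (SD) of 7.3" points for the change, which in turn rests on "SDs of 6% for each timepoint" and a pre/post correlation of 0.25. The Synopsis says that the figures were not adjusted for stratification. It also promises a linear model with the baseline value as a covariate; SAP 7.2 names no such covariate.

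**The concern.** The within-category contrasts are there to show whether the response differs by baseline fat, the reason SAP 2.2 gives for them. Neither document says how many patients each category should hold, what power a contrast inside it has, or how small a cell may be. The only planning figure that bears on this is the SD of 6 points, and it spreads patients too narrowly to fill categories that start 20 points apart.

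If an outer category holds one or two patients per arm, its contrast is reported as a test but can show almost nothing. A non-significant result there could be read as absence of effect at low or high baseline fat. Thin cells also trigger the move from the ANOVA to rank tests, which are at their weakest in such cells.

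**Working it through.** **Inputs.** From Protocol 12.1: 40 per arm, difference 5 points, SD 6 at each timepoint, r = 0.25, SD of change 7.3, two-sided 0.05. From SAP 7.2: the category limits. From SAP 2.2: 80 subjects at the interim. The documents give no baseline mean or shape, so both are assumptions here, and the mean is varied.

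**1. The plan's own figure.** SD of change = 6 × √(2 × (1 − 0.25)) = 7.35, stated as 7.3. Power with 40 per arm is 86.5% by the normal approximation and 85.7% by the noncentral t (85.2% with 7.35). The stated 85% reproduces.

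**2. Outer categories.** (30 − 10)/6 = 3.33 SD. Under normality the smaller of the two tails is largest when the mean is 20, where each tail is Φ(−10/6) = 0.0478. Then 40 × 0.0478 = 1.9 per arm, and at the interim (80/3) × 0.0478 = 1.3. Expected patients per arm at other means:

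| Assumed mean | ≤10% | ≥30% |
|---|---|---|
| 12 | 14.8 | 0.05 |
| 15 | 8.1 | 0.25 |
| 18 | 3.6 | 0.9 |
| 20 | 1.9 | 1.9 |
| 25 | 0.25 | 8.1 |

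A gamma shape with mean 20 and SD 6 gives 1.0 and 2.4. At mean 20 under normality, an outer category is empty in a given arm with probability (1 − 0.0478)^40 = 14%, and holds 4 or more with probability 12%.

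**3. Without any shape assumption.** Put a share a at 10, a at 30 and the rest at 20. The variance is 2a × 100 = 36, so a = 0.18 and each outer category can hold at most 40 × 0.18 = 7.2 per arm. Contrast power is then still only about 25%.

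**4. Power of a contrast inside a category.** Noncentrality = 5/(7.3 × √(2/n)), pooled error with about 108 df. At mean 20 with SAP limits, the expected n per arm is 1.9 / 20.7 / 15.4 / 1.9 and power is 10% / 59% / 47% / 10%. Using the smaller within-category SD of about 6.1–6.2 that SD 6 and r = 0.25 imply, the middle two rise to 73% and 62%. For 85%, a category needs about 39 per arm.

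**5. The rank fallback.** The smallest exact two-sided p for n v n is 2/C(2n, n):
- 2 v 2: 2/6 = 0.33
- 3 v 3: 2/20 = 0.10
- 4 v 4: 2/70 = 0.029
- 5 v 5: 2/252 = 0.0079
- 6 v 6: 2/924 = 0.0022

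A permutation test inside one category has the same floor. If the interim level of 0.00305 in SAP 9 applies to these tests, at least 6 v 6 is needed.

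**6. If the outer categories turn out well filled.** The baseline SD then exceeds 6. What follows for overall power (40 per arm, mean 20) depends on r and on the model:

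| Baseline SD | Each outer category, per arm | Power, r = 0.25, t-test | Power, r = 0.25, baseline covariate | r that keeps SD of change at 7.3 |
|---|---|---|---|---|
| 8 | 4.2 | 62% | 81% | 0.58 |
| 10 | 6.3 | 44% | 63% | 0.73 |
| 14.8 | 10.0 | 23% | 34% | 0.88 |

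**7. Continuous model.** Residual SD = 6 × √(1 − 0.25²) = 5.81. The SE of a dose difference at HFF 30%, with mean 20, is 5.81 × √(2/40 + 200/(39 × 36)) = 2.5 points. From 1.9 patients per arm alone it is about 6.0 (SD 5.81) to 7.5 (SD 7.3).

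**The case against.** The trial is declared exploratory, no power is claimed for any category, and Protocol 8.1 introduces HFF stratification for balance, not for subgroup testing. SAP 7.2 makes its ANOVA conditional on cell size, so thin cells were foreseen. That explains why nobody powered the categories. It does not explain why significance tests are specified in cells that may hold one or two patients. Appendix 1 has no 2 v 2 floor, but it pools over categories into one answer per dose and so leaves the question by category open.

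Three stronger readings are tempting, and the documents do not support them:

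- **Both outer categories hold about 2 per arm.** This needs a mean near 20 and a normal shape, and neither is stated. Elsewhere one outer category fills and the other nearly empties. Dropping normality raises the ceiling to 7.2 in each.
- **The within-category analysis cannot work at all.** The middle categories are underpowered, not impossible.
- **The planning statements contradict each other, or well-filled outer categories would make the 85% wrong.** Nothing in the documents says that the outer categories will be well filled. Power depends on the SD of change, which stays at 7.3 if the correlation is higher, and the baseline covariate promised in the Synopsis recovers part of any loss. A larger SD means that the 85% must be re-derived; it does not show that it fails.

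The continuous model also has limits. An SE of 2.5 gives a 95% interval of about ±5.0 points at HFF 30% (1.96 × 2.55), so about 50% power for 5 points, and that precision is borrowed from patients with middling baseline fat.

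**Conclusion.** The concern holds for the outer categories. Given the protocol's SD of 6 and a roughly normal baseline, at least one of them would hold about 2 or fewer patients per arm at any mean. The planned test there would have about 10% power or less, and the exact rank fallback could not reach 0.05 with 2 or 3 per arm. The interim is thinner still. In the middle categories the contrasts are weak, at 47–59% for mean 20 (62–73% with the smaller within-category SD). The normal shape is the main assumption; without it the outer cells could be larger, but their contrasts would still have only about 25% power. The 85% for the whole-arm comparison stands on its stated inputs. For an exploratory trial this is a change that should be made, and it does not threaten the primary comparison.

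**What to change.** In SAP 7.2, and for the interim in SAP 2.2 and 9, replace the tests within HFF categories by one ANCOVA of change in HFF with treatment, continuous baseline HFF and treatment-by-baseline HFF. Report each dose's difference from placebo with its confidence interval at HFF values fixed in advance, for example 10, 20 and 30%. This also restores the baseline covariate that the Synopsis promises. Keep the categories for descriptive tables only, collapsed where thin (for example at 20%). State what Appendix 1 is for, since it does not match the within-level tests in 7.2, and reconcile the middle cut-point, which is 20% in Protocol 8.1 and 21% in SAP 7.2.

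Separately, compute the baseline SD and the pre/post correlation from blinded pooled data. If the SD exceeds 6, re-derive the power for the model that will actually be used.

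The cost is SAP wording and one model. The downside is the assumed linear trend in effect over baseline HFF, which should be stated in the SAP.
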